2.4.5.2 Analyses of adverse events

Generalities

The primary focus of AE reporting will be on treatment-emergent adverse events (TEAEs). Pre- and post-treatment AEs will be described separately. The adverse events will be summarized by treatment group for the 26-week randomized treatment period and for FRC group for the whole

study treatment period including the 26-week single-arm extension period, respectively, unless specified otherwise.

If an AE date/time of onset (occurrence, worsening, or becoming serious) is incomplete, an imputation algorithm will be used to classify the AE as pre-treatment, treatment-emergent, or post-treatment. The algorithm for imputing date/time of onset will be conservative and will classify an AE as treatment-emergent unless there is definitive information to determine it is pre- or post-treatment. Details on classification of AEs with missing or partial onset dates are provided in [Section 2.5.3](#).

Adverse event incidence tables will present the number (n) and percentage (%) of patients experiencing an AE by primary SOC, HLGT, HLT and PT, sorted by the internationally agreed order for SOCs and alphabetic order for HLGT, HLT and PT within a SOC, for each treatment group. Multiple occurrences of the same event in the same patient will be counted only once in the tables within a treatment phase. The denominator for computation of percentages is the safety population within each treatment.

Sorting within tables should ensure the same presentation for the set of all AEs within the observation period (pre-treatment, treatment-emergent, and post-treatment). For that purpose, the table of all TEAEs presented by primary SOC and PT sorted by the internationally agreed order for SOCs and decreasing frequency for PTs within a SOC will define the presentation order for all other similar tables unless otherwise specified. Sorting of PTs will be based on the results for the FRC group.

The internationally agreed order of SOCs shown below was described in the Introductory Guide MedDRA Version 19.1, September 2016 International Conference on Harmonisation for SOC:

1. Infections and infestations
2. Neoplasms benign and malignant (including cysts and polyps)
3. Blood and lymphatic system disorders
4. Immune system disorders
5. Endocrine disorders
6. Metabolism and nutrition disorders
7. Psychiatric disorders
8. Nervous system disorders
9. Eye disorders
10. Ear and labyrinth disorders
11. Cardiac disorders
12. Vascular disorders
13. Respiratory, thoracic, and mediastinal disorders
14. Gastrointestinal disorders

15. Hepato-biliary disorders
16. Skin and subcutaneous tissue disorders
17. Musculoskeletal, connective tissue, and bone disorders
18. Renal and urinary disorders
19. Pregnancy, puerperium, and perinatal conditions
20. Reproductive system and breast disorders
21. Congenital and familial/genetic disorders
22. General disorders and administration site conditions
23. Investigations
24. Injury, poisoning, and procedural complications
25. Surgical and medical procedures
26. Social circumstances
27. Product issues

Analysis of all treatment-emergent adverse events

The following TEAE summaries will be generated for the safety population.

- Overview of TEAEs, summarizing number (%) of patients with any:
 - TEAE,
 - Serious TEAE,
 - TEAE leading to death,
 - TEAE leading to permanent treatment discontinuation;
- All TEAEs by primary SOC, showing number (%) of patients with at least 1 TEAE, sorted by internationally agreed order of primary SOCs;
- All TEAEs by PT, showing number (%) of patients with at least 1 TEAE, sorted by decreasing incidence of PT;
- All TEAEs by primary SOC, HLG, HLT and PT, showing number (%) of patients with at least 1 TEAE, sorted by SOC internationally agreed order. The other levels (HLG, HLT, PT) will be presented in alphabetic order;
- All TEAEs by primary SOC and PT, showing number (%) of patients with at least 1 TEAE, sorted by SOC internationally agreed order and decreasing incidence of PTs within a SOC. This sorting order will be applied to all other similar tables, unless otherwise specified;
- Common TEAEs (PTs with an incidence $\geq 2\%$ in any treatment group) by primary SOC, HLG, HLT, and PT, sorted by internationally agreed order of SOCs. The other levels (HLG, HLT, PT) will be presented in alphabetic order;

- All TEAEs regardless of relationship and related to IMP by primary SOC, HLGT, HLT, and PT, showing number (%) of patients with at least 1 TEAE, sorted by internationally agreed order of SOCs. The other levels (HLGT, HLT, PT) will be presented in alphabetic order;
- All TEAEs by maximal severity, presented by primary SOC and PT, showing number (%) of patients with at least 1 TEAE by severity (ie, mild, moderate, or severe), sorted by sorting order defined above;
- All TEAEs by primary and secondary SOC, HLGT, HLT, and PT, showing number (%) of patients with at least 1 TEAE, sorted by internationally agreed order of SOCs. The other levels (HLGT, HLT, PT) will be presented in alphabetic order;
- Kaplan-Meier curves will be provided, when appropriate, for the time to first onset of the following PTs: nausea and vomiting;
- The frequency of TEAEs over time will be provided for nausea and vomiting, using weekly time intervals up to 26 weeks, ie, [0-1] week, (1-2] weeks, (2-3] weeks, (3-4] weeks, etc. Similar summary will be also provided for the FRC group for the whole study treatment period including the extension period, using weekly intervals up to 52 weeks. In each time interval, the numerator in the calculation of percentages will be the number of patients with at least 1 TEAE occurring in this time interval. Two types of analyses will be included: (1) only the first event will be counted for each patient and all recurrent events will not be included, and the denominator for the calculation of percentages will be the number of patients at risk at the beginning of the time interval who did not experience a first event in the preceding intervals; and (2) the recurrent events in subsequent intervals will be counted once for each patient in the numerator of the corresponding interval, and the denominator for the calculation of percentages will be the number of patients at risk at the beginning of the time interval;
- Summaries of common TEAEs (PTs with an incidence $\geq 2\%$ in any treatment group) will be provided as appropriate by demographic factors including gender (Male, Female), age group (<50, ≥ 50 to <65, ≥ 65 to < 75, ≥ 75 years of age), and race (American Indian or Alaska Native, Asian/Oriental, Black, Native Hawaiian or Other Pacific Islander, White, Other), GLP-1 receptor agonist subtype (QD/BID formulations, QW formulations) at screening.
- Summaries of all TEAEs will be provided for FRC group respectively by anti-lixisenatide and anti-insulin glargine antibody status (Positive, Negative) during the 26-week randomized treatment period and during the whole study treatment period including 26-week extension period.

Analysis of all treatment emergent serious adverse event(s)

- All treatment-emergent SAEs by primary SOC, HLGT, HLT, and PT, showing the number (%) of patients with at least 1 treatment-emergent SAE, sorted by the internationally agreed SOC order. The other levels (HLGT, HLT, PT) will be presented in alphabetical order.

- All treatment-emergent SAEs regardless of relationship and related to IMP, by primary SOC, HLGT, HLT, and PT, showing the number (%) of patients with at least 1 treatment-emergent SAEs, sorted by the internationally agreed SOC order. The other levels (HLGT, HLT, PT) will be presented in alphabetical order.

Analysis of all treatment-emergent adverse event(s) leading to treatment discontinuation

- All TEAEs leading to treatment discontinuation, by primary SOC, HLGT, HLT, and PT, showing the number (%) of patients with at least 1 TEAE leading to treatment discontinuation, sorted by the internationally agreed SOC order. The other levels (HLGT, HLT, PT) will be presented in alphabetical order.

Local tolerability at injection site

The number (%) of patients with local intolerability at injection site will be summarized by PT (PTs coded from the investigator reported terms or PTs coded from ARAC diagnosis terms), sorted by decreasing incidence of PT. Similar summaries will be provided for FRC group respectively by anti-lixisenatide and anti-insulin glargine antibody status (Positive, Negative). All events will be listed.

Allergic reactions

Kaplan-Meier curves will be provided for the time to first onset of events adjudicated as allergic reactions by ARAC. The number (%) of patients with events adjudicated as allergic reactions by ARAC will be summarized by PT (sorted by decreasing incidence of PT) and ARAC diagnosis along with 2 subcategories, events adjudicated as possibly related to IMP and events adjudicated as not related to IMP. Tabulation summaries will be provided as necessary by gender (Male, Female), age group (<50, ≥50 to <65, ≥65 to <75, ≥75 years of age), race (American Indian or Alaska Native, Asian/Oriental, Black, Native Hawaiian or Other Pacific Islander, White, Other). Similar summaries will be provided for FRC group respectively by anti-lixisenatide and anti-insulin glargine antibody status (Positive, Negative).

All the allergic events reported by the investigator on the AE form for suspected allergic event and its associated complementary forms (confirmed or not confirmed by ARAC) will be listed.

Pancreatic-related events

- Increased pancreatic enzymes >2 times ULN
 - The number (%) of patients with events reported on the AE form for increased lipase and/or amylase >2 times ULN and its associated complementary forms will be summarized by PTs for each treatment group, sorted by decreasing incidence of PT.
 - The number (%) of patients with events positively adjudicated as pancreatitis by the PSAC will be summarized by type: 1) acute pancreatitis, 2) acute exacerbation of chronic pancreatitis, 3) chronic pancreatitis, 4) unknown pancreatitis.

- All events sent to PSAC for adjudication of pancreatitis (ie, events reported on the AE form for increased lipase and/or amylase > 2 times ULN) will be listed along with the adjudication outcome.
- Pancreatic neoplasm
 - All the events sent to PSAC for adjudication for pancreatic neoplasm will be listed along with the adjudication outcome including PSAC diagnosis, type of neoplasm (malignant, benign, not determined), cancer stage etc.

Increased calcitonin

The number (%) of patients with events reported on the AE form for increased calcitonin ≥ 20 pg/mL and its associated complementary forms will be summarized by PTs for each treatment group, sorted by decreasing incidence of PT in the FRC group. In addition, a listing of those patients will be provided.

ALT increase

The number (%) of patients with events reported on the AE form for ALT increase and its associated complementary forms will be summarized by PT for each treatment group, sorted by decreasing incidence of PT in the FRC group. In addition, a listing of those patients will be provided.

Device-related events

The number (%) of patients with events reported on device-related event questionnaire will be summarized for each treatment group along with 2 subcategories, events associated with a clinical event (either symptomatic hypoglycemic event or adverse event) and events not associated with a clinical event. The number of events and rates in patient year will also be summarized as appropriate. The number (%) of patients who have device-related events with lixisenatide dose $< 5 \mu\text{g}$, $> 20 \mu\text{g}$ within the corresponding time window (from event start date to event end date or to treatment end date if event end date is missing) of device-related event will be summarized for FRC group only. In addition, a listing of patients with those events will be provided.

Analysis of pre-treatment and post-treatment adverse events

- All pre-treatment AEs by primary SOC and PT, showing the number (%) of patients with at least 1 pre-treatment AE, sorted by the internationally agreed SOC order and decreasing incidence of PTs in the FRC group within each SOC.
- All post-treatment AEs by primary SOC and PT, showing the number (%) of patients with at least 1 post-treatment AE, sorted by the internationally agreed SOC order and decreasing incidence of PTs in the FRC group within each SOC.

Listings

Supportive AE listings will be provided for all AEs, SAEs and AEs leading to treatment discontinuation. These listings will include at least the following information, sorted by treatment, patient identification, and onset date: treatment, patient identification, country, age, gender, race, BMI, primary SOC, PT, reported term, onset date, study day (relative day to the start date of open-label treatment), AE duration, duration of exposure, intensity, corrective treatment, action taken with IMP, date of treatment discontinuation (if relevant), relationship to IMP/NIMP/study procedures, outcome, date of death (if any), seriousness, seriousness criteria, and AE status (“Pre” for a pre-treatment AE; “T” for a TEAE; and “Post” for a post-treatment AE).

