10.1.2.6 Post-treatment follow-up phone call visit for randomized treatment period

Post-treatment follow-up phone call visit is performed 3 (-1/+3) days following the last injection of the IMP (or 9 (-1/+3) days for patients receiving weekly GLP-1 RA). The visit is performed both for patients who completed the study and patients who withdrew from the study at the time of IMP discontinuation. The visit is NOT performed for patients who prematurely discontinued the IMP treatment and stay in the study. For patients continuing in the extension period, the visit is not performed in the randomized treatment period. This visit can be a phone call visit, or an on-site visit in case of ongoing or new adverse event during the post-treatment period, if necessary.

The patient is called by the Investigator or medically qualified designee at a certain, previously agreed time point.

During the phone call, the following questions are to be asked:

- Did you experience any new medical event, disease or symptom since the last visit?
- Did you experience any changes in a pre-existing medical condition, disease or symptom since the last visit?
- Did you change, take or add any new medications since the last visit?
- Did you experience any hypoglycemic symptoms or events?

All reports of hypoglycemic events (if any) or any adverse events are recorded. The use or change of any concomitant medications, including rescue therapy, is recorded.

IRT is contacted for notification of the end of study.

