10.3.4 Handling of patients after permanent treatment discontinuation

Patients will be maintained in the study as much as possible and followed-up according to the study procedures as specified in this protocol (except for the 3 day safety post-treatment follow-up assessment) up to the scheduled date of study completion, or up to recovery or stabilization of any AE requiring follow-up as specified in this protocol, whichever comes last.

If possible, after the permanent discontinuation of treatment regardless of the reason, the patients will be assessed as soon as possible using the procedure normally planned for the last dosing day

with the IMP (V28/End of randomized treatment visit for patients who discontinued the IMP before V28 (Week 26), or V35/end of extension treatment visit for patients who entered the extension period and discontinued the FRC before V35 (Week 52)).

For the meal test, please refer to [Section 9.2.1.2.2](#).

All cases of permanent treatment discontinuation should be recorded by the Investigator in the appropriate pages of the e-CRF and in the patient's medical records when considered as confirmed. IRT should be notified when a patient prematurely discontinues treatment.

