11.4.6.2 Analyses of adverse events

Pre-treatment AEs are AEs that developed or worsened or became serious pre-treatment period.

Treatment-emergent AEs (TEAEs) are AEs that developed or worsened (according to the Investigator's opinion) or became serious during the period from the administration of first dose of the study treatments up to 3 days (9 days for the weekly GLP1) after the last administration..

Post-treatment AEs are AEs that developed or worsened or became serious during the post-treatment period.

The primary focus of AE reporting in the CSR will be on TEAEs. Pre- and post-treatment AEs will be described separately.

All adverse events

Adverse event incidence tables will present by system organ class (SOC) (sorted by internationally agreed order), high-level group term (HLGT), high level term (HLT) and preferred term (PT) sorted in alphabetical order for each treatment group, the number (n) and percentage (%) of patients experiencing an AE. Multiple occurrences of the same event in the same patient will be counted only once in the tables within a treatment phase. The denominator for computation of percentages is the safety population within each treatment group.

Summaries of all TEAEs in each treatment group will include:

- The overview of AEs, summarizing number (%) of patients with any
 - TEAE;
 - serious TEAE;
 - TEAE leading to death;
 - TEAE leading to permanent treatment discontinuation;
- The number (n) and percentage (%) of patients with at least one AE by primary SOC, HLGT, HLT and PT;
- Summary of TEAEs by maximal severity (severe, moderate, mild), presented by primary SOC and PT;
- Summary of TEAEs possibly related to open-label IMP, presented by primary SOC and PT.

A detailed listing of TEAE summaries will be provided in the statistical analysis plan.

Death and serious adverse events

Death and treatment-emergent SAEs will be summarized and presented as number and percent of patients in each treatment group.

The following deaths summaries will be generated:

- Number (%) of patients who died by study period (TEAE, on-study) summarized on the safety population by treatment received;
- Death in nonrandomized or randomized and not treated patients;
- TEAE leading to death (death as an outcome on the AE e-CRF page as reported by the Investigator) by primary SOC, HLGT, HLT and PT showing number (%) of patients sorted by internationally agreed order of SOC and alphabetic order of HLGT, HLT, and PT.

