2.1.4 Safety endpoints

The safety endpoints are assessed by:

- Symptomatic hypoglycemia (documented, probable, severe symptomatic hypoglycemia),
- Adverse events (AEs), serious adverse events (SAEs), and AE of special interest (AESI),
- Safety laboratory values,
- Vital signs,
- Electrocardiogram (ECG).
- Immunogenicity (antibody variables, FRC group): anti-insulin and anti-lixisenatide antibodies.

Observation period

The observation period of safety data will be divided into 3 segments:

- The pre-treatment period is defined as the time between the date of the informed consent and the first injection of open-label IMP,
- The on-treatment period of the whole study for daily formulation is defined as the time from the first injection of open-label IMP up to 3 days (1 day for symptomatic hypoglycemia) after the last injection of IMP, regardless of the introduction of rescue

therapy. The on-treatment period of the whole study for weekly formulation is defined as the time from the first injection of open-label IMP up to 9 days (7 day for symptomatic hypoglycemia) after the last injection of IMP, regardless of the introduction of rescue therapy.

- The 26-week on-treatment period is defined as follows:
 - For patients who are not eligible to enter the extension period, the 26-week on-treatment period is defined as
 - For patients receiving daily IMP: time from the first injection of open-label daily IMP up to 3 days (1 day for symptomatic hypoglycemia) after the last injection of daily IMP, regardless of the introduction of rescue therapy.
 - For patients receiving weekly IMP: time from the first injection of open-label weekly IMP up to 9 days (7 day for symptomatic hypoglycemia) after the last injection of weekly IMP, regardless of the introduction of rescue therapy.
 - For the patients who are eligible to enter the extension period, the 26-week on-treatment period is defined as the time from the first injection of open-label IMP up to V28/Week 26 visit (or Day 183 if V28/Week 26 visit is missing).
- The post-treatment period is defined as the time starting 4 days (2 days for symptomatic hypoglycemia) after the last injection of open-label daily IMP, or starting 10 days (8 days for symptomatic hypoglycemia) after the last injection of open-label weekly IMP (after the on-treatment period of the whole study).

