2.3.2 Safety population

The safety population consists of all randomized patients who receive at least 1 dose of open-label IMP (regardless of the amount of treatment administered). Patients will be analyzed for safety analyses according to the treatment actually received.

In addition:

- Nonrandomized but treated patients will not be part of the safety population; however, their safety data will be presented separately;
- Randomized patients for whom it is unclear whether they took the IMP will be included in the safety population as randomized;
- When a patient is exposed to both FRC and GLP-1 receptor agonist, the patient will be analyzed in the treatment group (FRC or GLP-1 receptor agonist) in which he/she is treated longer;
- Patients will be excluded from the safety population only if there is documented evidence (ie, all study dates recorded as no medication taken) that patients have not taken the study medication.

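### Post-treatment adverse events are shown only as a percentage of the whole safety population, which cannot be separated from the rate of stopping treatment

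*SAP*

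**What the plan says.** SAP 2.4.5.2 specifies the table as "All post-treatment AEs by primary SOC and PT, showing the number (%) of patients with at least 1 post-treatment AE". It gives the table neither its own denominator nor a rate, so the general rule at the start of that section applies: "The denominator for computation of percentages is the safety population within each treatment". Protocol 11.4.6.2 has the same rule: "The denominator for computation of percentages is the safety population within each treatment group". Membership of that population requires one dose and no observation after treatment: "The safety population consists of all randomized patients who receive at least 1 dose of open-label IMP" (SAP 2.3.2).

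The timing is set elsewhere:

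- **Start of the period (SAP 2.1.4).** "The post-treatment period is defined as the time starting 4 days (2 days for symptomatic hypoglycemia) after the last injection of open-label daily IMP". For weekly products it opens at day 10.
- **Patients who finish treatment (Protocol 10.1.2.6).** "Post-treatment follow-up phone call visit is performed 3 (-1/+3) days following the last injection of the IMP", or at day 9 with the same window for weekly GLP-1 RA.
- **Patients who stop early (Protocol 10.3.4).** "Patients will be maintained in the study as much as possible and followed-up according to the study procedures", until their planned end of participation. Protocol 10.4.2 keeps AE recording open over that time.
- **FRC patients in the extension.** SAP 2.1.4 places the post-treatment period after the on-treatment period of the whole study, so these patients have not reached it at Week 26.

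**The concern.** A table of n (%) reads as a risk when the patients in the denominator were watched for the event over roughly similar times. Here most of the denominator is hardly watched at all, while a minority is followed for weeks or months. The printed figure then depends on how many patients stopped and stayed under observation, as well as on what happened to them.

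Two things are at stake. The level understates the risk among patients who stopped. And if the arms differ in stopping, the table can show a gap where the risks are equal, or hide one where they differ.

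The primary HbA1c analysis deliberately uses values obtained after IMP discontinuation (SAP 2.4.4.1), so safety over the same follow-up should be readable for the patients who supplied it. The SAP already handles other safety data this way. SAP 2.4.5 bases abnormality percentages on patients assessed in the period. The weekly-interval tables for hypoglycemia, nausea and vomiting use patients at risk (2.4.5.1, 2.4.5.2). Hypoglycemia is also given per patient-year (2.4.5.1).

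**Working it through.** **Inputs**

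- 250 patients per arm and 20% drop-out (SAP 1.3). The protocol synopsis calls the rate common to both arms.
- About 230 FRC patients expected in the extension (protocol synopsis), so 20 of 250 = 8% do not enter. This serves as a lower stop rate. It also includes patients barred for other reasons.
- Period start at day 4 (daily) or day 10 (weekly); completers' last call at day 2 to 6 or day 8 to 12.
- AE risk after stopping: not in the documents. 30% is assumed, with a range below.

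**The plan's own figure.** The documents give no figure for post-treatment AEs. The sample size that supplies 250 and 20% can be reproduced. The diluted effect is 0.4 × (1 − 0.20) = 0.32; with SD 1.1, two-sided 5% and 90% power, this needs 249 per arm by the normal approximation and 250 by the t-test (power 90.1%). It agrees with the plan.

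**Who is observed after treatment.** Assume stops spread evenly over 182 days, with follow-up to day 182.

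- Mean post-treatment days per early stopper: daily (182 − 3)² / (2 × 182) = 88.0; weekly (182 − 9)² / (2 × 182) = 82.2.
- Days per completer: 0 at the nominal call; at the late edge 6 − 4 + 1 = 3 (daily) or 12 − 10 + 1 = 3 (weekly).
- If the weekly call is timed from Week 26 (Protocol 6.1 and flow chart footnote a) and the last dose was 6 days before that visit, the latest call is on day 6 + 12 = 18. That gives 18 − 10 + 1 = 9 days.

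Share of post-treatment person-time from early stoppers:

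| Completers' call | 20% stop | 8% stop |
|---|---|---|
| Nominal day | 100% | 100% |
| All at late edge, daily | 50×88.0 / (50×88.0 + 200×3) = 88% | 20×88.0 / (20×88.0 + 230×3) = 72% |
| All at late edge, weekly | 87% | 70% |
| Weekly extreme, 9 days | 50×82.2 / (50×82.2 + 200×9) = 70% | 20×82.2 / (20×82.2 + 230×9) = 44% |

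In the FRC arm, patients entering the extension contribute nothing to the 26-week table.

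**What the percentage measures.** Ignoring the small completer term, printed % = stop rate × risk after stopping.

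| Stop rates | Risk after stopping | Printed on 250 per arm |
|---|---|---|
| 20% and 20% | 30% and 30% | 15/250 = 6.0% and 15/250 = 6.0% |
| 8% and 20% | 30% and 30% | 6/250 = 2.4% and 15/250 = 6.0% |
| 8% and 20% | 30% and 12% | 6/250 = 2.4% and 6/250 = 2.4% |

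The dilution is 1/0.20 = 5-fold at 20% stopping. The gap in the second row is 0.20/0.08 = 2.5-fold whatever the common risk: at 10% it prints 0.8% and 2.0%, at 50% it prints 4.0% and 10.0%.

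**On the patients observed.** With completers called on the nominal day and all stoppers followed, the second row becomes 6/20 = 30% and 15/50 = 30%.

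**The case against.** Much of the case on the other side stands.

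- **Risk does enter the figure.** A reader might infer that the table shows only how many stopped. It does not: the percentage is a product of the two, and the trouble is that they cannot be pulled apart.
- **A false gap needs unequal stopping.** A reader might infer that the table will favour one arm. The documents do not support that, because the plan assumes a common 20%. The 8% comes from the expected extension entry, and the 30% risk is illustrative.
- **Not every stopper supplies long follow-up.** Protocol 10.1.2.6 provides the short call for patients who leave the study when they stop IMP. They add about as little as completers.
- **Weekly completers may add more than 3 days**, as the extreme case shows.
- **Part of the answer is already planned.** The table prints counts, SAP 2.2 tabulates discontinuations by arm, and the AE listings flag post-treatment events with study day and discontinuation date. A reader could approximate events per stopper, but not a rate per patient-year.
- **A stoppers-only denominator should not replace the present one.** Patients who stopped are selected after randomization, and the share of all treated patients with such an event is a legitimate description. This argues for adding figures.

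**Conclusion.** The point holds as a cheap improvement. The denominator rule and the follow-up schedule together give a percentage in which stop rate, remaining follow-up and risk after stopping are mixed. No post-treatment AE table in the SAP separates them.

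At the plan's own equal 20% stopping, the consequence is a level about five times below the risk after stopping, with no false difference. A 2.5-fold gap from identical risks arises only if the arms stop at rates as far apart as 8% and 20%. These results assume that stoppers remain under observation and that completers add almost no time. The second assumption is weakest for weekly GLP-1 RA.

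Severity is minor. Treatment-emergent events are the main focus, safety is descriptive without testing (SAP 2.4.5), and no planned conclusion rests on this table.

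**What to change.** In SAP 2.4.5.2, keep the existing percentage for post-treatment AEs and add by arm:

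1. the number of patients with any post-treatment observation;
2. the percentage on that number;
3. the total post-treatment follow-up time;
4. events per post-treatment patient-year.

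Present these within the split that SAP 2.4.5.2 already plans: both arms for the 26-week period, FRC only for the whole study. Items 3 and 4 are needed beside item 2 because a completer with a late call enters that denominator with only a day or so.

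Separately, reconcile the timing of the follow-up call for weekly GLP-1 RA. Protocol 6.1 and flow chart footnote a count from Week 26, while Protocol 10.1.2.6 counts from the last injection.

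The cost is one derived variable (post-treatment days per patient) and a few table rows. The downside is that the added percentages rest on fewer patients, are less precise, and describe a subset formed after randomization, so the table should stay descriptive.
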